Based on estimates of the number of vulnerable infants fulfilling the criteria of inclusion and the need of minimum two CHNs educated in the PUF-VIPP method per municipality, a total of 49 CHNs have been educated in the VIPP-PUF method since June 2021. The VIPP-PUF education consists of a four-days course including teaching in the theoretical basis of the VIPP, building on attachment theory and theories of mentalization and social learning, as well as the developmental approach of the PUF-program integrating case-based learning and practical exercises. The initial VIPP-PUF course is followed by training in using the VIPP-PUF intervention to parents of a child aged 9 to 12 months, notably a child without problems and from a non-vulnerable family. During this training the CHNs receive individual supervision in groups by a certified supervisor from the VIPP- Institute, Leiden, the Netherlands, delivered before each of the five home visits in the training period. Next the CHNs receive a one-day booster course in the VIPP-PUF method around one week ahead of intervention start in their municipality. During her first VIPP-PUF intervention to a vulnerable child, the CHN receives two sessions of individual supervision by a certified supervisor, alternating with peer-supervision in groups led by experienced VIPP-PUF CHNs. The evaluation of the VIPP-PUF intervention includes an evaluation of the needs of educating specific Danish VIPP-PUF supervisors in collaboration with the VIPP Institute, this to ensure the sustainability of the VIPP-PUF training and supervision during the project period and beyond.

Development of intervention components

The specific tools and activities of the intervention will be developed in a participatory planning group and in dialogue with the Project Steering Group.

Educational experts, graphic- and web-designers, videographers and writers will be consulted to develop the web-platform and extended scripts, plans, visual and written outlines (booklets, leaflets/handouts/newsletters) and video demos (visual presentation of information, skills training, and case situations).

Focus discussions involve CHNs from the study area and parents, recruited by local CHNs (WP4).

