Dose delivered	The amount of the intended units of intervention delivered by the intervention providers, e.g., number of conducted home visits.	Data will be collected through CHNs' self-monitoring checklists for each VIPP-PUF intervention session.
Fidelity	Information on the extent to which the intervention was implemented and delivered as planned (quality and integrity of the intervention delivery), including information on adaptations and reasons for adaptations.	Data will be collected through leading CHNs' recordings and through CHNs' self-monitoring checklists for each VIPP-PUF intervention session relating to all main elements of the VIPP-PUF intervention as described in the manual. Examples include the specified video recordings during daily situations at home visits; themes of the program delivered for each session and successively elaborated during the intervention period; the CHNs' use of the manualized instruction for feed-back to the parents; and the delivery of written material on sensitive parenting including sensitive responding in daily situations about e.g., eating and feeding. Also, fidelity is explored through participant observations of 10-15 home visits where the program is used and through interviews with the CHNs (see p.15-17 for elaboration of the qualitative methods).
Participant responsiveness	Information on participants' (receivers and providers) receptiveness and acceptability, how they respond to, are engaged by, and enact an intervention, their enthusiasm and interest, their judgement about the outcome, relevance, and usefulness and how far they accept the responsibility of the intervention and holds the attention.	Data will be collected through questionnaires to parents and CHNs as well as through individual interviews with parents and CHNs.

INFANT HEALTH

Barriers and facilitators of participation	Knowledge on what barriers and facilitators CHNs and parents experience when participating in VIPP-PUF.	Data on what families and CHNs experience as either facilitating or hindering their participation in the intervention will be collected through questionnaires and individual interviews with both parts.
--	---	---

Interview guides will be developed for both the focus groups and the semi-structured individual interviews. Interviews will be audio-recorded and transcribed verbatim and anonymized (231).

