4.2 Statistical analyses

Statistical analyses will be carried out according to the intention to treat principle, where the participants are analyzed according to their CAU/intervention recruitment group. For continuous outcomes (including the primary outcome measured as the SDQ total difficulties score), linear mixed models will be fitted to compare the control group receiving care as usual (CAU) and the VIPP-PUF intervention group. For binary outcomes (e.g., border line/abnormal versus normal SDQ score), logistic mixed-effects regression models will be fitted to compare the control and intervention groups. All models include municipality-specific random effects, allowing for the correlation between outcomes of children from the same municipality. Likewise, cluster-specific random effects will be included.

Differences in weight-for-length between intervention and control groups will be evaluated using analysis of covariance (ANCOVA). Associations between weight-for-length z-score and selected risk factors based on their associations with infant behavior and preschool obesity in the published literature will be explored using linear regression. To assess differences in parental feeding practice and infant eating behavior between intervention and control groups, mean scores on the feeding and eating questionnaires subscales are calculated and analyzed using linear mixed models for repeated measurements, including participant-specific random effects. Further, exploratory analyses regarding feeding practices, eating behavior, and weight development will be carried out.

Other prognostic factors identified from the literature *á priori* will be included in analyses. Examples include parents’ education, employment status, household income, ethnicity, parental age, parental mental health problems and marital status (all obtained from national registers) (160); at the child level, sex, birth parameters, weight-for-length z-scores from birth to age 9 months, regulatory problems from ages 2-9 months, and ASQ:SE2 score at 9-10 months; and at the

INFANT HEALTH

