municipality level, e.g., level of social disadvantage. Interaction terms will be included to explore possible differences in intervention effect (on the primary outcome SDQ score only) between gender, pre-defined subgroups based on weight-for-length z-scores 0-9 months, low versus high scores of regulatory problems 2-9 months (0-2 problems versus ≥ 3 problems of eating, sleep or emotional dysregulation); low versus high baseline ASQ:SE2 scores and parental characteristics. Also, additional analyses of effect modification will further explore the effect by different population groups (socio-economic position, family structure, and migration status).

We will use path analysis to explore whether the effect of the intervention on weight-for-length z-score at age 18 and 24 months is mediated through the above-mentioned risk factors for childhood overweight. Using path analysis, we can assess the direct effect of the intervention, corresponding to the proportion not mediated through risk factors for child overweight, and the indirect effects of the intervention, corresponding to the proportion mediated through selected risk factors for childhood overweight. The total effect is the sum of the direct and indirect effects.

(Please see the WP4 protocol, WP 4b (Version January 2022) for further details regarding the statistical analyses of the process evaluation).

Sample size re-calculation

Based on recent research (239), an updated sample size calculation has been carried out for testing the primary outcome (the SDQ total score). The mean SDQ total score at the baseline, in children with ≥ 3 problems, is expected to be 13 (182) and the intervention group is now expected to reduce the mean SDQ total score to 11 (179). Consequently, to detect a difference in the SDQ total score of 2 while assuming a standard deviation of 5.7 (239), a small cluster effect (assuming an intraclass correlation of 0.001 as there are only 3 large clusters involved), and a significance level of 0.05 and with 80% power, we need a total sample size of 306 participants (240) (21). We expect a participation rate of 85% at the baseline and a 30% dropout rate by the 24-month follow-up assessment, leaving a total of 460 children available for assessments of the primary outcomes, conditioned a recruitment of about 780 children at baseline.

5 Ethics

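### Section 4.2 has no term for the treating VIPP-PUF nurse, so any between-nurse variation in delivery is left out of the standard error of the intervention effect

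*Protocol*

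**What the plan says.** Section 4.2 fits linear or logistic mixed models by intention to treat: "All models include municipality-specific random effects, allowing for the correlation between outcomes of children from the same municipality". A second random effect is for cluster. Section 3.2 uses that word for the three groups of municipalities (6+5+5) and also for the municipalities themselves, never for nurses. The feeding and eating models add a participant effect. Neither document's section 4.2 has a nurse term, a nurse ICC or a nurse-level sensitivity analysis.

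The sample size rests on "to detect a difference in the SDQ total score of 2 while assuming a standard deviation of 5.7", with a cluster allowance described as "assuming an intraclass correlation of 0.001 as there are only 3 large clusters involved".

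On delivery, section 3.5 names the nurse's training and supervision in video feedback as the active ingredient and reports that "a total of 49 CHNs have been educated in the VIPP-PUF method since June 2021", with at least two per municipality. Section 3.2 offers VIPP-PUF in the intervention phase only; control families receive the nurses' usual care. The process evaluation (section 3.8, Table 1) measures dose and fidelity partly through nurses' "self-monitoring checklists for each VIPP-PUF intervention session".

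**The concern.** One nurse delivers the whole programme to a family. If nurses differ in how well they deliver it, outcomes of children treated by the same nurse are correlated. The protocol plans to study such variation in delivery but leaves it out of the outcome model.

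In a parallel cluster trial, a municipality random effect would largely cover this, because each municipality would be in one condition. Here every municipality contributes both conditions. A shared municipality intercept cancels from the before-and-after contrast within a municipality; variance that arises only under VIPP-PUF does not. It makes the treatment contrast itself vary between municipalities, and nothing in the model represents that. If nurses do differ, the standard error is too small, and chance differences among a few nurses can pass for an effect of the programme.

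**Working it through.** **The plan's own figure.** The plan states "a significance level of 0.05 and with 80% power, we need a total sample size of 306 participants". Per arm, taking alpha as two-sided, n = 2 × (1.960 + 0.842)² × 5.7² / 2² = 127.5, so 256 in total. A total of 306 implies a design effect of about 306/256 = 1.20. With ICC 0.001 that means a mean cluster size of about 192–201. The plan does not state this size. Its own counts come close: 780 × 0.7 / 3 = 182 gives 1 + 181 × 0.001 = 1.181 and a total of 301–304. So 306 is reproduced within rounding, and it contains no nurse component.

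**Caseload (derived, not stated).** With 85% participation and 30% dropout, 780 × 0.85 × 0.70 = 464 children would be analysed; the plan rounds this to 460. With all 49 nurses active and equally loaded:
- 40% of 460 in the intervention condition: 184/49 = 3.8
- 50% of 460: 230/49 = 4.7
- 60% of 460: 276/49 = 5.6
- 60% of the 471 reported available in October 2024 (section 3.1): 283/49 = 5.8

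**Simple variance formula.** Take m = 4.7, an even split and nurse ICC ρ (an assumption). The intervention-arm design effect is 1 + (m − 1)ρ. The contrast inflation is its average with 1. Required N is 306 times the inflation. Power is for a difference of 2 and SD 5.7 at N = 460, with no municipality or period terms.

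| ρ | Arm design effect | Contrast inflation | Type I error if ignored | Required N | Power at 460 |
|---|---|---|---|---|---|
| 0 | 1.00 | 1.00 | 5.0% | 306 | 0.964 |
| 0.02 | 1.07 | 1.04 | 5.4% | 317 | 0.959 |
| 0.05 | 1.18 | 1.09 | 6.1% | 334 | 0.950 |
| 0.10 | 1.37 | 1.18 | 7.2% | 363 | 0.933 |
| 0.20 | 1.74 | 1.37 | 9.4% | 419 | 0.895 |

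Uneven caseloads raise these figures. With a coefficient of variation of 0.6, type I error is 6.6% at 0.05 and 8.2% at 0.10. The wedge itself makes loads uneven: with equal steps and three nurses per municipality, 460/64 = 7.2 children per municipality-step gives about 7.2, 4.8 and 2.4 children per nurse in the first, second and third groups.

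**Simulation in the wedge.** 16 municipalities, three step groups, 48 nurses, N = 460, nurse variance in intervention children only, REML with a municipality intercept and no nurse term, 4,000 runs per setting (Monte Carlo SE about 0.4 points):

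| ρ | Type I error, as written | Empirical SE / model SE | Type I error, period effects added |
|---|---|---|---|
| 0 | 4.9% | 0.551 / 0.541 | 5.9% |
| 0.02 | 6.0% | 0.564 / 0.542 | 5.6% |
| 0.05 | 7.2% | 0.586 / 0.543 | 6.6% |
| 0.10 | 9.6% | 0.630 / 0.545 | 6.7% |
| 0.20 | 11.6% | 0.685 / 0.547 | 8.3% |

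The model SE barely moves while the true spread grows; at ρ = 0.10 it is 0.630/0.545 = 1.16 times the reported SE. Other simulations, with different municipality sizes and a municipality ICC of 0.02, give 6–7.8% at ρ = 0.05 and about 9% at 0.10 as written. With step effects fitted they give 6.4–7.0% at 0.05–0.10. At ρ = 0 the range is about 5–6% with or without step effects.

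**Subsample outcomes.** Body composition (50 children) and coded video (100) have about 25/49 = 0.5 and 50/49 = 1.0 intervention children per nurse at an even split. If they are spread across nurses, there is almost no within-nurse clustering to model.

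**The case against.** The strongest reply is that the correlation may be slight. Sessions are standardised and manual-based, and nurses receive certified and peer supervision, all of which narrows differences. The outcome is parent-rated at 24 months, about a year after a three-month programme. At ρ = 0.10 the between-nurse SD would be √0.10 × 5.7 = 1.8 points; around the planned 2-point benefit, about 13% of nurses would then make children worse. This argues for the lower half of the ICC range, and it stands. It does not show that ρ is zero.

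Control children are also seen by nurses, and section 5 says video feedback is already common among Danish nurses, so nurse clustering need not be absent in the control phase. That also stands. The gap in the model concerns the extra variance specific to VIPP-PUF.

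Some of the inflation has other sources. With period effects, the error rate is already 5.9% at ρ = 0, so the excess of about 0.8 points at 0.05–0.10 is barely distinguishable from simulation noise. In that model, using t with 14 degrees of freedom and no nurse term brings the rate to 4.0–4.7%. As section 4.2 is written, though, it mentions no period term, and there a nurse effect alone returns the rate to about 5%.

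A reader might infer that outcomes are modelled as fully independent, or that the standard error is too small on every outcome. The documents support neither. Independence is conditional on municipality and step group, and the shortfall requires nurses to differ and does not extend to the subsample measures.

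**Conclusion.** The point holds as a modest weakness in the analysis model. The plan makes no provision for variation between VIPP-PUF nurses, and the municipality intercept does not supply it. As written, the two-sided type I error is about 6% at a nurse ICC of 0.02, 6–8% at 0.05 and 9–10% at 0.10; with period effects it is about 6–7% at 0.05–0.10.

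These figures assume the nurse ICC, the arm split, and that about three nurses per municipality are all active. It would be tempting to state as fact that 49 nurses each treat about five study children. The documents give the number trained, not the number active or their caseloads.

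Nor should it be read as a power problem. On the simple calculation, power at 460 stays near 0.90 even at ρ = 0.20, although with very uneven caseloads the scaled requirement there reaches 471. That calculation leaves out period adjustment, which is a separate question. The separate WP4 protocol and the published design paper were not available to check.

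**What to change.** In section 4.2, for the primary and other full-sample outcomes, add a random effect for the treating VIPP-PUF nurse in the intervention condition only (a partially nested model), with small-sample degrees of freedom such as Kenward–Roger for the linear models. Report the estimated nurse ICC. The subsample outcomes do not need it.

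First confirm that nurse identity is recorded and can be linked to outcomes. The session checklists are the natural source, but the documents do not say that they carry an identifier. If it cannot be linked, or the model does not converge, use a municipality-by-intervention random slope, which needs no nurse identifier.

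Families who decline VIPP-PUF have no treating nurse. Keep them in the intention-to-treat set as singletons; the nurse who made the offer may not be one of those trained.

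The cost is a few sentences of SAP text and, if the identifier exists, a data merge. Intervals widen slightly if nurses differ, and one more variance component has to be estimated from few children per nurse. Fix the choice before outcomes are analysed, so that it cannot look data-driven.

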The outbreak of the COVID pandemic in the beginning of March 2020 has had an immense influence on the study-flow and the recruitment rate in the participating municipalities, which at times has ranged from 70% in some municipalities to zero in others. Consequently, we have had to extend the overall study period including the recruitment period, and strong efforts have been made to intensify the recruitment in the individual municipalities. The PUF-program education to correctly identify the vulnerable children, has thus been boosted, delivering regular brush-up courses by special educated project CHNs. A total of seven of these project CHNs have been allocated to the Infant Health Study, to further intensify the identification of children meeting the criteria of inclusion, and specifically, to intensify the support to the CHNs in municipalities having low rates of recruitment.

During 2021-2022, the recruitment aims have been adjusted. Firstly, the launch of the recruitment period has been postponed to August 16, 2021, and next, the period of recruitment has been extended to October 31, 2023. Based on the frequency of children identified with three or more vulnerabilities so far, we have adjusted the overall expected identification rate from 16 pct. to 10 pct. of the screened children, with some municipalities recruiting up to 70 % of what we expect, while others only recruit 30% or even less. Still, throughout the recruitment period we have realized a relatively high rate of participation among eligible children invited for participation.

Per October 2022, the recruitment aims are adjusted to comprise around 780 children at baseline, and around 460 children available for the follow-up at 24 months (see Figure 1).

For further sample size justification please see section 4.2.

Supplementary information October 2024

June 2024-october the data collection in project was forced to pause caused by discrepancies in the ethical evaluations completed by the Research Ethics Committee REC University of Southern

INFANT HEALTH

Denmark in 2020 and 2022, and the local Committees on Health Research Ethics in the Capital Region of Denmark June 2024. After approval of the project continuation in the remaining period of data collection from the local Committees on Health Research Ethics, research activities were re-up taken October 2024.

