3.2 Design

We have chosen the stepped wedge cluster randomized design (163-165) mainly for two reasons. First, it is more feasible to randomize at the municipality level as compared to the level of the individual child or CHN. An RCTs based on randomization of the individual child or nurse would be associated with more logistical demand on the individual municipality or nurse as compared to the stepped wedge design as they would be having both the intervention and the control condition running simultaneously. For practical reasons, all municipalities cannot be trained at the same time but have to be split into three groups, and with the stepped wedge design we utilize this and randomly allocate the 16 participating municipalities to the time at which their health nurses have been trained and start offering the intervention to families. Also, with the SWD spill over is reduced by the randomization of clusters as compared to individual randomization. Second, in the stepped wedge design, interventions are introduced in a stepwise manner to all participating clusters (municipalities in this case) which encourages participation for those who would otherwise have been randomized to the control condition. Initial feedback from our interactions with the municipalities reveals that their motivation is strongly associated with being able to offer the intervention, as many municipalities prioritize early intervention highly. Also, with the stepped wedge design control families are recruited in the early phases of the trial, which enhances the recruiting of a control group with the level of usual care offered at the beginning of the trial. In the control period no participants receive intervention and sequential random crossover to the intervention cannot be reversed (166).

An important advantage of the stepped wedge design is that families only need to consent to participate in a research study and not to be randomized. In our experience this makes a big difference not only to the families, but also the front personnel who are recruiting the families. With a longer recruitment period and higher expected acceptance rates, the stepped wedge design will

INFANT HEALTH

[figure not shown]

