result in a larger sample size and less frustration about recruitment among the CHNs who find it very hard to deliver standard care to families, when they have introduced an intervention, they believe is superior. Thus, we believe that the stepped wedge design is associated with the least dropout.

On a practical level, the 16 participating municipalities will be randomly distributed into three clusters (6+5+5), and clusters will be randomized to initiate intervention at three different time points, according to the stepped-wedge design (see Figure 1, flow diagram revised October 2022) (Detailed overview of the design, see Appendix 1).

Figure 1. CONSORT diagram

INFANT HEALTH

Randomization and screening (PUF) at child-age 9-10 months

According to the randomization of municipalities, all children assessed to have ≥ 3 problems will function as controls and receive care as usual from Step 0 until the municipalities initiate the intervention in Step 1- 3, respectively.

Recruitment of municipalities, children, and parents

INFANT HEALTH

[figure not shown]
All municipalities that have implemented the basic PUF-program are invited, and the leading CHNs from the becoming study municipalities are invited to join the study planning group as key stakeholders.

In the participating municipalities, the parents of children becoming 9-10 months in the study period are informed about the project by the CHNs, and via written folders and information on the study home page (<https://www.sdu.dk/da/sif>). At the scheduled home visit at child ages 9-10 months, the CHNs complete PUF-assessment and offer the parents feedback in accordance with the basic PUF-program and the existing routines. All parents of children who have been assessed to have three or more problems are offered extended service, in the control phase of the study this is delivered in accordance with the existing routines of the CHNs in the particular municipalities (care as usual), whereas the CHNs offer the VIPP-PUF intervention to parents in the intervention phase. The CHN informs all parents of infants full-filling the study criteria of inclusion about the details in the Infant Health project, and if parents are interested, they are invited for participation by e-post. Parents make their final agreement for participation by answering the web-based questionnaires at the study website.

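### The primary model puts a random effect on what are most naturally three groups and omits a municipality-by-step term and a small-sample test, so its standard error can be too small if municipality outcomes vary between steps

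*Protocol*

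**What the plan says.** Section 4.2 (same text in the Protocol and in the Combined protocol and SAP) specifies the primary analysis of the SDQ total score as follows: "linear mixed models will be fitted to compare the control group receiving care as usual (CAU) and the VIPP-PUF intervention group". On correlation it says: "All models include municipality-specific random effects, allowing for the correlation between outcomes of children from the same municipality". The next sentence is: "Likewise, cluster-specific random effects will be included".

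Section 3.2 uses the word cluster in two ways. On the practical set-up: "the 16 participating municipalities will be randomly distributed into three clusters (6+5+5), and clusters will be randomized to initiate intervention". In the argument for the design: "interventions are introduced in a stepwise manner to all participating clusters (municipalities in this case". The sample size paragraph of section 4.2 counts three large clusters. Since municipality already has its own random effect, the added one is most naturally for the three groups.

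The design has four periods. Controls "receive care as usual from Step 0 until the municipalities initiate the intervention in Step 1- 3, respectively". Section 4.2 names no random effect for municipality by step, no degrees-of-freedom method, no permutation test and no fixed step effect.

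**The concern.** Two features of the random structure do not fit a stepped wedge with 16 randomised municipalities.

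First, the three groups are only the randomised order of starting. A random effect for them asks for a variance from three values, and it represents no identified source of correlation beyond municipality.

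Second, each municipality changes from control to intervention during recruitment, which by section 3.1 ran from 16 August 2021 to 31 October 2023, about 26 months. Much of the comparison is therefore made within municipality over time. A constant municipality intercept treats two children recruited two years apart in one municipality as being as alike as two recruited in the same step. If a municipality's SDQ level moves between steps, part of that movement enters the treatment contrast without entering its standard error. The confidence interval and p-value for the primary outcome, and for other outcomes analysed with this structure, would then be too optimistic.

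**Working it through.** **The plan's own figure.** Per arm, n = 2 × (1.96 + 0.84)² × 5.7² / 2² = 127.5 with unrounded normal quantiles, or 255.0 in total. The stated 306 follows with the parallel-cluster design effect 1 + (m − 1) × 0.001 at m = 200: 255.0 × 1.199 = 305.8. The documents state no m, so 200 is inferred. It is close to 780 × 0.70 / 3 = 182 (giving 302) and 780 × 0.85 / 3 = 221 (giving 312), which supports the reading of three large clusters.

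**Three levels.** Even if the three group effects were observed without error, a 95% interval for their variance on 2 df runs from 2/7.38 = 0.27 to 2/0.0506 = 39.5 times the estimate.

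**The omitted term.** Inputs from the documents: SD 5.7 (variance 32.49), 460 children, 16 municipalities, four steps. Assumed: the ICC, the share of it that is step-specific, and a two-sided z test at 1.96, because the plan names no reference distribution. Let the step-specific variance be w = 32.49 × ICC × share and the child-level variance e = 32.49 × (1 − ICC). With equal cells there are 460 / (16 × 4) = 7.19 children per municipality and step. A model without the step-specific term pools w into the residual, so approximately

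reported SE / true SE = √[(e + w) / (e + 7.19w)], and type I error = 2 × [1 − Φ(1.96 × ratio)].

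At ICC 0.05 with half step-specific, w = 0.812 and e = 30.87. The ratio is √(31.68 / 36.70) = 0.929, and type I error is 6.9%.

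This was compared with REML simulations under no effect: 1,500 runs per setting, Monte Carlo error about 0.6 points at 5%, unequal municipality sizes, and the stated municipality and three-group random effects. Paired values are without / with fixed step effects.

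| ICC | Step-specific share | SD of step-specific part (SDQ points) | Hand ratio | Simulated ratio | Simulated type I error |
|---|---|---|---|---|---|
| 0.001 | none | 0 | 1.000 | 0.98 / 0.99 | 5.3% / 4.9% |
| 0.001 | half | 0.13 | 0.998 | 0.98 / 0.98 | 5.7% / 5.9% |
| 0.05 | none | 0 | 1.000 | 0.99 / 0.99 | 5.3% / 5.1% |
| 0.05 | one fifth | 0.57 | 0.969 | 0.97 / 0.95 | 5.3% / 5.7% |
| 0.05 | half | 0.90 | 0.929 | 0.91 / 0.90 | 8.2% / 8.6% |
| 0.10 | one fifth | 0.81 | 0.939 | 0.93 / 0.94 | 7.3% / 7.1% |
| 0.10 | half | 1.27 | 0.869 | 0.86 / 0.87* | 9.3% / 8.9%* |

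*Analytic generalised least squares with a municipality effect only; not simulated.

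**What the three-group term does.** With step effects at ICC 0.001 and no step-specific part, the mean SE is 0.827 with the term and 0.803 without it. It widens the interval slightly.

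**After the change.** With fixed step effects and random effects for municipality and municipality-by-step, reported SE over true SD is 0.97 to 1.05, and z-test type I error is 4.0% to 6.2% over the simulated settings. A fixed t(14) reference multiplies the critical value by 2.145 / 1.96 = 1.094 and gives 2.4% to 4.0%, which is conservative.

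**The case against.** The strongest reply is that nothing goes wrong at the only ICC the documents give. At 0.001 the error rate is nominal within simulation error. Material inflation needs an ICC at least 50 times larger and a sizeable step-specific share of it. That stands, and it makes the consequence conditional. It does not make 0.001 a safe basis for the test: the plan justifies that value by the small number of clusters, which says nothing about how alike children within one are, and it cites no estimate from data.

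Several stronger readings are tempting, and the documents do not support them.

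- *The three-group effect makes the error bars too narrow.* It does not; it slightly widens them. It can also be fitted. It was estimated as zero in 59–68% of fits, but its true value there was zero, so this is ordinary boundary behaviour. The municipality-by-step variance was also estimated as zero in 26–61% of fits, and the proposed model then falls back to a municipality intercept.
- *Section 3.1 shows drift within municipalities.* It says of the recruitment rate: "which at times has ranged from 70% in some municipalities to zero in others". That is mainly a spread between municipalities, which a municipality intercept absorbs, and it concerns recruitment rather than SDQ. The boosted identification training and the extra nurse support for low-recruiting municipalities are plausible reasons for case mix to shift, but the documents do not quantify any shift.
- *The plan uses a Wald z test.* It names no reference distribution. That is a gap in specification. Without step-specific variance the choice between z and t matters little, because the contrast is largely within municipality.

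Planned adjustment for baseline ASQ:SE2 score, family factors and municipality disadvantage may also remove part of any case-mix shift; the calculations include no covariates.

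**Conclusion.** The point holds in conditional form. The plan specifies a random effect that most naturally has three levels and serves no clear purpose, and it leaves out the term that protects a stepped-wedge contrast against step-to-step variation within municipality. A reader might infer that the 0.05 level is already lost; the calculations do not show that. The loss is negligible at ICC 0.001 and small at ICC 0.05 with one fifth step-specific (about 5.3–6%). It is material at ICC 0.05 with half step-specific or at ICC 0.10: SE about 6–14% too small, type I error about 7–9%. These ICC and persistence values are assumptions. In SDQ units the material settings correspond to step-specific SDs of about 0.8 to 1.3 points, against a target difference of 2.

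The missing fixed step effect is a separate and larger matter. At 460 children and ICC 0.001, adding one raises the SE from 0.53 to 0.79 and lowers power for 2 points from 96% to about 72%.

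**What to change.** In section 4.2 of both documents:

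1. Define the word cluster and use it in one sense throughout.
2. Delete the random effect for the three groups.
3. Specify random effects for municipality and for municipality-by-step, alongside fixed step effects.
4. For the primary test, name Kenward-Roger or Satterthwaite degrees of freedom, or a permutation test that re-randomises the 16 municipalities 6+5+5 (16! / (6! 5! 5!) = 2,018,016 allocations). Do not fix t(14), which is conservative.
5. Use the same random structure for the binary models.

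This takes a few sentences, written before analysis. Compared with a municipality intercept alone, the SE is about 3–10% larger over most of the range when step-specific variation exists (for example 0.849 to 0.908 at ICC 0.05 with half step-specific), and about 15% larger at the most extreme setting tried (0.881 to 1.009). The critical value is slightly larger. Where there is no such variation the cost is small: the mean SE goes from 0.803 to 0.822 at ICC 0.001.
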